7.4.2 Modifications of Study Therapy

A dose will be considered as actually delayed if the delay is exceeding 3 days. It is defined as duration of previous cycle in days -14. Dose delays will be divided into the following categories: on-time, 4-7 days, 8-14 days, 15-42 days, >42 days. Reason for dose delay will be retrieved from CRF dosing pages.

The nivolumab infusion can be interrupted and/or the IV infusion rate can be reduced. This information will be retrieved from CRF dosing pages.

The following parameters will be summarized:

- Number of subjects with at least one dose delayed
- Number of dose delayed per subject, length of delay, and reason for dose delay.
- Number of subject with at least one dose infusion interrupted along with reason for the interruptions and number of infusions interrupted per subject.
- Number of subjects with at least one infusion with IV rate reduced along with the reason of the rate reduction and number of IV rate reduced per subject.

[REDACTED]

[REDACTED]

[REDACTED]

[REDACTED]

[REDACTED]

7.5 Efficacy

7.5.1 Secondary Analyses

7.5.1.1 Overall Survival and Objective Response Rate

Overall survival is defined as the time between the start of treatment and the date of death due to any cause. A subject who has not died will be censored at last known date alive. OS will be followed up while subjects are on the study drug and every 3 months via in-person or phone contact after subjects discontinue the study drug.

Overall survival will be summarized using Kaplan-Meier (KM) product limit method for all treated subjects by subgroups based on ECOG PS (PS 0-1 and PS 2). Median values of OS, if estimable, along with 2-sided 95% CI using the Brookmeyer and Crowley method will be calculated. If medians are not estimable, other percentiles (eg, 10th and 25th) may be reported. OS rates at selected time points, including survival rates at Years 1 and 2, together with their 95% CIs will also be estimated using KM estimates on the OS curves. Minimum follow-up must be longer than the timepoint of interest to generate the OS rate for that particular timepoint. For example, if the timepoint of interest is 9 months and the interval of enrollment date and last patient last visit is less than 9 months, then, the minimum follow-up is not reached and OS rate is not generated. Associated 2-sided 95% CIs will be calculated using the Greenwood formula.

Objective Response Rate is defined as the number and percentage of subjects with a best overall response (BOR) of confirmed CR or PR. ORR as assessed by the investigator will be reported. The ORR will be summarized by binomial response rates and their corresponding two-sided 95% exact CIs using the Clopper-Pearson method. This analysis will be performed for all response evaluable subjects and by subject ECOG PS subgroups. In addition, the BOR will also be summarized according to response category. A by subject listing will be provided.

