Mandatory tumor assessments are to be completed at Weeks 9 and 52 (±5 days). Additional tumor assessments should be performed as required by local standards of care or at the investigator’s discretion as discussed in the Time and Events Schedule and are recommended every 8-12 weeks until disease progression per RECIST 1.1 criteria (or discontinuation of study treatment in subjects receiving nivolumab beyond progression), subject lost to follow up, withdrawal of study consent by subject, or end of study. Overall survival will be collected for at least 3 years and up to 5 years from the first dose of study therapy, as indicated in the assessment tables.

Statistical Considerations:

Sample Size: A total of 950 subjects who are evaluated based on the ECOG PS will be enrolled; Subgroup 1 will enroll subjects with PS 0-1 (n ~ 855), and Subgroup 2 will enroll subjects with PS 2 (n ~ 95). The screen failure rate is anticipated to be 15%, which results to approximately 719 and 81 treated subjects in Subgroup 1 and Subgroup 2, respectively.

With n=800 subjects, about 4 subjects will experience a rare adverse event with 0.5% true cumulative event rate with a rate estimate within a 95% confidence interval (CI) (0.1%-1.3%). Approximately 2 subjects with events and a 95% CI of (0.1%-0.9%) for assumed true event rate of 0.25% are projected.

The 95% CI is calculated using the Clopper-Pearson method in PASS12.

Endpoints: The primary endpoint is the incidence of high-grade (CTCAE v4.0 Grades 3-4), treatment-related, select adverse events

The secondary endpoints include:

- Incidence of high grade (Grades 3-4) select adverse events
- Median time to onset and median time to resolution (Grades 3-4) of select adverse events
- OS
- ORR

Analyses: The analysis of primary, secondary (excluding objective response rate), and exploratory endpoints will be reported for the full safety analysis set and subgroups based on ECOG PS. ORR will be reported for the response evaluable analysis set and by PS subgroups and randomized cohorts

Analysis of Primary Endpoints

The number and percentage of subjects who report high-grade (Grades 3-4), treatment-related, select adverse events will be summarized for all treated subjects and by subgroups. Treatment-related, select adverse events will be tabulated using worst grade per NCI CTCAE V4.0 criteria by system organ class (SOC) and Medical Dictionary for Regulatory Affairs (MedDRA) preferred terms.

Analysis of Secondary Endpoints

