8.2 Populations for Analyses

- All enrolled subjects: all subjects who signed an informed consent form and were registered into the IVRS.
- All treated subjects: all subjects who received any nivolumab. This is the primary population for safety and efficacy analyses. Subpopulation analyses will be conducted by subject PS subgroups.
- All response evaluable subjects: all treated subjects who have baseline and at least one on-study evaluable tumor measurement.

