8.4 Analyses

The analysis of primary, secondary (excluding ORR), and exploratory endpoints will be reported for the full safety analysis set, and by subgroups based on ECOG PS. ORR will be reported for the response evaluable analysis set and by PS subgroups.

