8.4.2.2 Secondary Analyses

The number and percentages of subjects who report high-grade (Grades 3-4) select adverse events, regardless of relationship to treatment, will be summarized for all treated subjects by subgroups and randomized subjects. Select adverse events will be tabulated using worst grade per NCI CTCAE V4.0 criteria by SOC and MedDRA preferred terms. In addition to reporting number and percentages of subjects with select adverse events, 95% confidence intervals (CIs) for incidence density rates will be provide based on the Poisson distribution

In addition, descriptive statistics for time to onset and time to resolution of select adverse events will be estimated using Kaplan-Meier (KM) product limit method for all treated subjects and by subgroups. Median time to onset and median time to resolution, if estimable, will be presented together with their 95% CI using Brookmeyer and Crowley method. If medians are not estimable, other percentiles (eg, 10th or 25th) may be reported.

[REDACTED]

8.4.3 *Efficacy Analyses*

OS is defined as the time between the start of treatment and the date of death due to any cause. A subject who has not died will be censored at last known date alive. OS will be followed up while subjects are on the study drug and every 3 months via in-person or phone contact after subjects discontinue the study drug.

OS will be summarized using Kaplan-Meier (KM) product-limit method and associated statistics for the treated analysis set. Median values of OS, if estimable, along with 2-sided 95% CI using the Brookmeyer and Crowley method will be calculated. If medians are not estimable, other percentiles (eg, 10th and 25th) may be reported. OS rates at selected time points, including survival rates at Years 1 and 2, together with their 95% CIs will also be estimated using KM estimates on the OS curves. Associated 2-sided 95% CIs will be calculated using the Greenwood formula. OS summary statistics indicated earlier for the treated analysis set will be reported by subgroups.

The ORR will be summarized by binomial response rates and their corresponding two-sided 95% exact CIs using the Clopper-Pearson method. This analysis will be performed for all response evaluable subjects. This analysis will also be performed by subject subgroups.

[REDACTED]

[REDACTED]

[REDACTED]

[REDACTED]

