4.2 Secondary Endpoints

The secondary endpoints include:

- Incidence of high grade (Grade 3-4) select adverse events
- Median time to onset and median time to resolution (Grades 3-4) of select adverse events
- OS is defined as the time from first dosing date to the date of death. A subject who has not died will be censored at last known date alive. OS will be followed continuously while subjects are on treatment and every 3 months via in-person or phone contact after subjects discontinue the study drug.
- ORR is defined as the number and percentage of subjects with a best overall response (BOR) of confirmed CR or PR with respect to all treated subjects. ORR as assessed by the investigator will be reported.

[REDACTED]

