6.3 Populations for Analyses

- All enrolled subjects: all subjects who signed an informed consent form and were registered into the IVRS.
- All treated subjects: all subjects who received any nivolumab. This is the primary population for safety and efficacy analyses.
- All response evaluable subjects: all treated subjects who have baseline and at least one on-study tumor measurement.

See section 7.1 for the subpopulation details.

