7 STATISTICAL ANALYSES

7.1 General Methods

In the analysis described below (except where noted), counts and percentages will be reported for discrete variables with inclusion of unknown or missing values as a separate category. The mean, standard

deviation, median, range (minimum and maximum), and number of non-missing values will be reported for each continuous measure.

Adverse events and medical history will be coded according to the most recent Medical Dictionary for Regulatory Activities (MedDRA). Previous and concomitant medications will be coded using the WHO Drug Dictionary.

The time to event distribution (i.e overall survival and duration of response) will be estimated using Kaplan Meier techniques. Median for time to event endpoints along with 95% confidence interval (CI) will be constructed based on 95% CI using the Brookmeyer and Crowley method. OS rates at selected time points, including survival rates at Years 1 and 2, together with their 95% CIs will also be estimated using KM estimates on the OS curves. Associated 2-sided 95% CIs will be calculated using the Greenwood formula.

The analysis of primary, secondary (excluding objective response rate), and exploratory endpoints will be reported for the treated population and subgroups based on ECOG PS (PS 0-1 and PS 2). ORR will be reported for the response evaluable analysis set and by ECOG PS subgroups.

SAS® version 9.2 or higher will be used for statistical analyses, tabulations and graphical presentations.

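### ORR is defined over all treated subjects in SAP 4.2 but estimated only in response-evaluable subjects in SAP 7.1 and 7.5.1.1, which normally raises it

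*SAP*

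**What the plan says.** **Pointing to all treated subjects**

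- SAP 4.2 defines the endpoint as the number and percentage with a "best overall response (BOR) of confirmed CR or PR with respect to all treated subjects".
- SAP 6.3 and protocol 8.2 each name all treated subjects as the main population for efficacy as well as safety.

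**Pointing to response-evaluable subjects**

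- SAP 7.1: "ORR will be reported for the response evaluable analysis set and by ECOG PS subgroups".
- SAP 7.5.1.1, on the ORR and its two-sided 95% Clopper-Pearson interval: "This analysis will be performed for all response evaluable subjects and by subject ECOG PS subgroups".
- Protocol 8.4: "ORR will be reported for the response evaluable analysis set and by PS subgroups". Protocol 8.4.3: "This analysis will be performed for all response evaluable subjects". The synopsis names the same set.

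**Neutral**

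- Protocol 8.3.2 and the restated definition in SAP 7.5.1.1 give no denominator.

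**The evaluable set itself** is worded in two ways. SAP 6.3 has "all treated subjects who have baseline and at least one on-study tumor measurement"; protocol 8.2 has "all treated subjects who have baseline and at least one on-study evaluable tumor measurement". Only the protocol requires the measurement to be evaluable.

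**Other response output.** SAP 7.5.1.1 plans a summary of best overall response (BOR) by category, without naming a population for it. SAP 7.1 asks for missing or unknown values to be shown as their own category. SAP 7.5.2.1 plans a by-subject listing of tumour response in treated subjects. SAP 9 refers to a Data Presentation Plan for the full list of analyses; that plan was not available.

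**The concern.** A programmer who follows SAP 4.2 and one who follows SAP 7.5.1.1 will produce different headline figures for the same endpoint.

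The denominator actually specified is also the one more open to selection. Membership is decided by events after the first dose. The first mandatory on-study scan is at Week 9 (protocol 5.4), and other scans follow local practice or the investigator's judgement. A treated subject who dies or deteriorates without any on-study scan is removed from the denominator. That subject would ordinarily count as a non-responder, so the removal normally moves the estimate upwards.

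ORR is one of the stated secondary objectives and is reported by performance status (PS), so the figure will be read and quoted even though no hypothesis is attached to it.

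**Working it through.** **Inputs from the documents**

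- Enrolled: 950; screen failures: 15%; treated: about 800 (protocol 8.1, SAP 5).
- Interval: two-sided 95% Clopper-Pearson (SAP 7.5.1.1).
- First mandatory on-study scan: Week 9 (protocol 5.4).

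**Inputs that the documents do not give, so assumed**

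- p, the ORR in all treated subjects: 15%, with 10% and 20% as alternatives.
- d, the share of treated subjects outside the evaluable set: 5% to 30%.
- r, the response rate among those excluded: 0 in the main illustration.

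**Step 1. The plan's own figure.** 950 x (1 - 0.15) = 807.5, which agrees with the stated figure of about 800. I use 800 as the all-treated denominator.

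**Step 2. Formula.** Of N treated subjects, pN respond. Removing dN subjects, of whom r x dN respond, leaves

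reported ORR = (p - d x r) / (1 - d).

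With r = 0 this is p/(1 - d). It exceeds p whenever r is below p and equals p only when r = p or d = 0.

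**Step 3. Numbers at p = 15%, r = 0.** All treated: 120/800 = 15.0% (95% CI 12.6 to 17.7).

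| d | Evaluable n | Reported ORR | 95% CI | Factor 1/(1 - d) |
|---|---|---|---|---|
| 5% | 760 | 120/760 = 15.8% | 13.3 to 18.6 | 1.05 |
| 10% | 720 | 120/720 = 16.7% | 14.0 to 19.6 | 1.11 |
| 20% | 640 | 120/640 = 18.8% | 15.8 to 22.0 | 1.25 |
| 30% | 560 | 120/560 = 21.4% | 18.1 to 25.1 | 1.43 |

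At d = 5% or 10% the reported value lies inside the all-treated interval. At d = 20% it lies above that interval's upper limit.

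**Step 4. Other values of p, at d = 20%.** 80/800 = 10.0% becomes 80/640 = 12.5%. 160/800 = 20.0% becomes 160/640 = 25.0%. The factor is 1.25 in each case.

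**Step 5. Can the direction reverse?** Only if those excluded respond more often than treated subjects overall (r above p). Protocol 3.3.1 admits clinically apparent disease that the investigator follows, so a responder without a recorded measurement is conceivable. At d = 10% and p = 15%, however, 0.15 x 80 = 12 of the 80 excluded subjects would have to be responders just to cancel the shift. Protocol 5.4 asks for evaluation by RECIST 1.1, which makes that unlikely.

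**The case against.** **The operative instruction is clear, and the odd phrase occurs once.** SAP 7.1, SAP 7.5.1.1, the protocol synopsis, 8.4 and 8.4.3 all name the evaluable set. A specific rule for ORR can override a general statement about populations, so one could simply strike the phrase in SAP 4.2. It is true that the SAP's ORR analysis follows the protocol's. But striking the phrase would leave a denominator selected on post-treatment events, and neither document explains why ORR should depart from the main efficacy population.

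**All-treated response data may be tabulated anyway.** The BOR summary has no population of its own, and the missing-category rule could give an all-treated table with a missing row. That reading is possible but not certain, because the preceding sentence in SAP 7.5.1.1 names the evaluable set. A reader might infer that the plan offers nothing on all treated subjects beyond a listing; the BOR summary means the documents do not support that. What no visible text plans is an all-treated ORR with a confidence interval. The Data Presentation Plan might.

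**A reader can recompute it.** Given the responder count and the number treated, the point estimate follows, provided no responder falls outside the set. The exact intervals, overall and by PS, would still have to be worked out by hand.

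**The consequence is limited.** This stands. ORR is secondary, no decision rule on it is visible, the sample size is logistical and SAP 7.7 plans no interim analysis. At small d the shift is modest.

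**Conclusion.** The point holds. The SAP contradicts itself on the ORR denominator, and both documents carry the tension between all treated subjects as the main efficacy population and an ORR computed in a subset. It would be tempting to call this purely a SAP error against a consistent protocol; protocol 8.2 rules that out.

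The direction is upwards as long as excluded subjects respond less often than treated subjects overall, which is the ordinary case. The size is p/(1 - d) when none of them respond: a relative increase of 5%, 11%, 25% or 43% at d = 5%, 10%, 20% or 30%. Those values of d and the 15% ORR are assumptions, so the documents support the direction and the formula but no particular amount of inflation.

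A reader might also infer that the comparison of PS 0-1 with PS 2 is distorted. That would follow if d differed between the subgroups, but the documents give no d for either, so it remains a possibility. Nor does the point touch the primary safety endpoint or overall survival, which do not use the evaluable set.

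It should be fixed, as a matter of moderate weight.

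**What to change.** **SAP**

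- In 7.1 and 7.5.1.1, make ORR with its Clopper-Pearson interval in all treated subjects, overall and by PS, the main estimate, in line with 4.2 and 6.3. Count treated subjects without an on-study assessment as non-responders.
- State that the BOR summary is in all treated subjects, with a row for not evaluable or missing.
- Keep the response-evaluable ORR beside it as a labelled supportive analysis, so that the SAP still delivers the analysis the protocol specifies. Give the number excluded by PS.
- Use one definition of the evaluable set in both documents, settling whether the on-study measurement must itself be evaluable.

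**Protocol, at its next revision**

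- Align the synopsis, 8.4 and 8.4.3 with 8.2.

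**Cost.** Some wording and one extra table. The by-subject response listing in treated subjects is already planned, so no new data are needed. The headline ORR will normally be somewhat lower.

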7.5.1.2 Subject Follow-up for OS

The extent of follow-up defined as the time between enrollment date and last known date alive (for subjects who are alive) or death date (for subjects who died) will be summarized descriptively (median, min, max) for all subjects treated.

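### The follow-up summary in SAP 7.5.1.2 counts death as the end of follow-up, so at a mature cut its median restates median OS instead of showing how long subjects could have been observed

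*SAP*

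**What the plan says.** SAP 7.5.1.2 (Subject Follow-up for OS) defines the measure: "The extent of follow-up defined as the time between enrollment date and last known date alive (for subjects who are alive) or death date". It "will be summarized descriptively (median, min, max) for all subjects treated".

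OS uses the same end dates but a different start. SAP 4.2: "OS is defined as the time from first dosing date to the date of death". SAP 7.5.1.1: "Overall survival is defined as the time between the start of treatment and the date of death due to any cause", and "A subject who has not died will be censored at last known date alive".

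SAP 7.5.1.1 also has a separate rule for landmark rates: "Minimum follow-up must be longer than the timepoint of interest to generate the OS rate for that particular timepoint". Its worked example withholds a 9-month rate if "the interval of enrollment date and last patient last visit is less than 9 months". That is a calendar interval, which deaths do not shorten.

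Protocol 3.1 calls OS a key endpoint and closes the study once the last enrolled subject has at least 3 years of follow-up. The Protocol Synopsis has survival collected for 3 to 5 years from first dose. The SAP text available contains no reverse Kaplan-Meier, survivors-only or potential follow-up summary.

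**The concern.** A follow-up figure is printed beside a survival curve so that the reader can judge how far along the curve the data are mature. That requires the time for which subjects could have been observed. In the planned measure a subject who dies at month 4 contributes 4 months, however long that subject would have been watched. The result therefore depends mainly on the death rate: the worse the survival, the shorter the follow-up appears.

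The minimum has the same weakness. SAP 7.5.1.1 uses the term minimum follow-up for a calendar interval, whereas the minimum reported under 7.5.1.2 is the shortest individual time to death or last contact. A reader who compares the two could wrongly conclude that the condition for a Year 1 or Year 2 rate had not been met.

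A smaller point is that follow-up starts at enrollment and OS at first dose, so the two are not on one clock.

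**Working it through.** The plan states no figure for extent of follow-up, so there is none to reproduce.

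**Inputs from the documents**
- Minimum follow-up at closure: 36 months (Protocol 3.1).
- Gap from enrollment to first dose: taken as 0 to 28 days, from the screening window in SAP 2.1. With the SAP section 8 factor, 28 / 30.4375 = 0.92 month.
- Treated subjects: about 800 (950 × 0.85 = 807.5; SAP section 5).

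**Assumptions (not in the documents)**
- Exponential OS with median 6, 9, 12 or 15 months.
- Uniform accrual over 12 or 18 months.
- Loss to follow-up of 0% or 5% per year.
- Gap to first dose uniform over 0 to 28 days.
- Survivors known alive at the cut-off.

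**Step 1: the median, for any survival distribution.** Let T be survival from first dose, C the time to censoring, and X = min(T, C). If nobody is censored before 36 months, then for every t < 36, X > t exactly when T > t. If median OS is below 36 months, the median of X therefore equals median OS.

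**Step 2: add the gap.** The planned measure is X + U, with U the enrollment-to-dose gap. A gap uniform over 0 to 0.92 month averages 0.46 month. Median OS of 6, 9 or 12 months then gives about 6.46, 9.46 or 12.46.

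**Step 3: potential follow-up.** Its median is 36 + accrual/2, that is 36 + 6 = 42 months or 36 + 9 = 45 months.

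**Step 4: simulation** (800 subjects, 60 replicates per scenario, 36-month minimum; all in months):

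| Assumed median OS | Planned median, 12-mo accrual | Planned median, 18-mo accrual | Planned median, 12-mo accrual, 5%/yr loss | KM median OS, 12-mo accrual | Reverse-KM median, 12 / 18-mo accrual | Planned max, 12 / 18-mo accrual |
|---|---|---|---|---|---|---|
| 6 | 6.49 | 6.54 | 6.29 | 6.02 | 41.96 / 45.38 | 45.73 / 49.35 |
| 9 | 9.47 | 9.51 | 8.95 | 9.02 | 41.83 / 45.21 | 47.89 / 53.16 |
| 12 | 12.57 | 12.46 | 11.66 | 12.14 | 41.94 / 45.13 | 48.42 / 53.96 |
| 15 | 15.50 | 15.71 | 14.04 | 15.07 | 41.92 / 45.00 | 48.43 / 54.30 |

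With the gap set to zero, the planned median and the KM median agree within 0.03 month. With 5% yearly loss, the reverse-KM median is 40.8 to 41.2 months at 12-month accrual. The planned minimum is 0.1 to 0.2 month throughout, against a calendar minimum of 36.

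**Step 5: earlier cuts** (12-month accrual, no loss):

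| Minimum follow-up | Assumed median OS | Planned median | KM median OS | Reverse-KM median |
|---|---|---|---|---|
| 3 | 9 | 6.17 | 9.01 | 8.99 |
| 6 | 12 | 8.76 | 12.03 | 12.01 |
| 12 | 15 | 13.48 | 14.83 | 18.00 |

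When minimum follow-up is shorter than median OS, the planned figure no longer matches median OS. It falls below both median OS and actual follow-up.

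**The case against.** The strongest reply is that SAP 7.5.1.1 already protects the landmark rates. A Year 1 or Year 2 rate is produced only if a calendar-based minimum is exceeded, so its appearance tells the reader that the minimum was met. The planned summary also includes the maximum, about 46 to 54 months in the scenarios above for median OS of 6 to 12 months, which would stand beside the short median. The measure is openly defined, and its median errs towards too little follow-up, so it cannot make immature data look mature. All of this stands.

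A reader might infer that the maturity of the OS rates could not be judged at all. The documents do not support that, because of the 7.5.1.1 rule and the maximum. What remains is that the rule gives a yes or no per timepoint and no printed number, and the maximum describes a single subject.

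A reader might also infer that the OS results are biased. They are not: the Kaplan-Meier analysis handles censoring properly, and neither it nor the 7.5.1.1 rule uses this summary. Nor does the planned median always reproduce median OS; Step 5 shows that it does not at early cuts.

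The difference in clocks is real in the text but small. It is at most 28 days if enrollment falls within the screening window, and could be less: SAP 2.2 enrolls subjects after eligibility is established, although the sample-size section counts screen failures among the 950 enrolled.

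**Conclusion.** The point holds as a reporting defect. At a mature cut, with median OS below 36 months and little early loss, the planned median carries no information beyond median OS plus a gap of about half a month. For assumed median OS of 6 to 12 months it reads about 6.5 to 12.5 months where potential follow-up is 42 to 45 months. At 12-month accrual that is too low by a factor between 42/12.57 = 3.3 and 42/6.49 = 6.5. The planned minimum is not the quantity that SAP 7.5.1.1 calls minimum follow-up.

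The equality in Step 1 does not depend on the shape of the survival curve. The sizes do depend on the assumed median OS, accrual time, loss and enrollment-to-dose gap. Follow-up contacts every 3 months would place some last known alive dates before the cut-off and lower the reverse-KM figure somewhat.

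No OS estimate, confidence interval or decision changes. The change is worth making because OS is called a key endpoint and a planned number does not serve its purpose.

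**What to change.** In SAP 7.5.1.2:

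1. Measure follow-up from first dose, as for OS.
2. Report median follow-up by reverse Kaplan-Meier: deaths censored at the date of death, subjects alive counted as events at the last known alive date.
3. Print the minimum potential follow-up, from first dose of the last treated subject to data cut-off. Word the 7.5.1.1 rule on the same interval, since its example starts at enrollment and ends at last patient last visit.
4. Keep the present median, minimum and maximum only if labelled observed time on study.

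Item 3 matters most if nearly all subjects have died. At an assumed median OS of 6 months about 99% are dead at closure, so the reverse-KM median rests on roughly 0.01 × 800 = 8 survivors.

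The cost is a change of SAP wording and a few lines of programming. No new data are needed.
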